### 7.1.1. Baseline Definition

The day of Ad-RTS-hIL-12 administration is designated as Day 0. Baseline value for safety and demographic data is defined as the last non-missing value closest, but prior to, the first dose of study drug veledimex or Ad-RTS-hIL-12. For tumor assessment, a baseline MRI will be performed within 72 hours of Ad-RTS-hIL-12 administration (Day 2).

### 7.1.2. Analysis Visit Window

For safety parameters excluding clinical laboratory data, measurements collected from unscheduled visits will NOT be included in the by-visit summary tables but will be included in the listings. Early termination visits for safety measurements will not be mapped to any scheduled post-baseline visit but will be used as the last assessment during the treatment period.

## 7.2. Data Handling

### 7.2.1. Age

For partial dates of birth with both the month and day missing, the month and day will be set to June 30. Completely missing dates of birth will remain as missing, with no imputation applied. Consequently, the age of the subject will not be calculated and will remain missing. In listings of demographic data, the partial dates of birth as entered will be displayed.

### 7.2.2. Safety Data Handling

For all safety data, only observed data will be used for analyses, and missing data will not be imputed.

### 7.2.3. Handling of Repeated Clinical Laboratory Tests

For laboratories results at unscheduled visits, it will be treated as repeated laboratory results for the closest previous visit. The last repeat of laboratory results will be used in the summary tables for that visit. All the laboratory test results (original test results and repeated results) will be included in the data listings.

### 7.2.4. Handling of Partial Dates for AEs

When determining the AE, partial start dates of AEs will be assumed to be the closest possible date to date of first dose and are consistent with the partial date. Imputation of partial dates is used only to determine whether an event is treatment-emergent; data listings will present the partial date as recorded in the eCRF.

- A completely missing onset date will be coded as the date of first dose. If the resulting onset date is after a reported date of resolution, the onset date will be set equal to the date of resolution.
- If year is present, but both month and day are missing, or month is present, and day is missing,
  - if year < year of first dose date, then set missing month to December and missing day to last day of the month.
  - if year > year of first dose date, then set missing month to January and missing day to 1st day of the month.
  - if year = year of first dose date, then set missing month to the month of first dose and missing day to the day of first dose.
- If year and month are present, but day is missing,
  - if date of year and month < date of year and month of first dose, then set missing day to last day of the month.
  - if date of year and month > date of year and month of first dose, then set missing day to 1st day of the month.

- if date of year and month = date of year and month of first dose, then set missing day to the day of first dosing.
- For all other cases, set the date to date for first dose.

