## **13. SAFETY ANALYSIS**

### **13.1. Adverse Events (AEs)**

AEs will be coded using MedDRA and will be classified by SOC and PT of MedDRA. All AEs will be captured up through day 56.

Severity: The severity of AEs will be assessed according to the NCI CTCAE v. 4.03 ranging from Grade 1 to Grade 5.

TEAE: A treatment emergent AE (TEAE) is defined as any AE that begins, or any preexisting condition that worsen in severity during the treatment period. For determination of TEAEs during the treatment period, AEs with the greatest severity before baseline will be used as a benchmark for comparison of AEs occurring captured up through day 56.

Relationship (Causality): AEs that have possibly, probably or related relationship to the study drug are defined to be Related to the study drug. Otherwise, the AE will be defined as Not Related. AEs for which the relationship to the study drug is missing will be considered as related to the study drug. AEs with the closest relationship to the study drug will be used for the summary.

TEAEs will be tabulated by subject ID in listings by treatment arm and dose cohort, SOC and PT according to the relationship to study drug(s), the severity and seriousness for the OSP. The following types of TEAEs will be provided:

- Overview of TEAEs
- TEAEs by SOC and PT
- TEAEs by SOC, PT, and Maximum CTCAE toxicity grade
- TEAEs by SOC, PT, and Maximum CTCAE toxicity grade  $\geq 3$
- TEAEs by PT in decreasing frequency
- Drug-related TEAEs by SOC and PT
- Drug-related TEAEs by PT in decreasing frequency
- Serious TEAEs by SOC and PT
- TEAEs leading to death by SOC and PT
- TEAEs leading to treatment discontinuation by SOC and PT

- TEAEs leading to dose interruption by SOC and PT
- TEAEs leading to dose reduction by SOC and PT

If the same PT or SOC is reported more than once for a subject, the subject will only be counted once in the corresponding incidence of PT or the SOC.

To avoid overcounting events for a given PT or SOC, only the most severe and the most closely related PT and/or SOC term will be included for each subject ID in tabulations by severity (i.e., CTCAE toxicity grade) and relationship.

For all subjects in the OSP, AEs, serious AEs and AEs leading to treatment discontinuation will be listed by the subject ID, by the treatment arm and the dose cohort.

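### SAP 7.2.4 puts an AE onset with a missing day under two conflicting imputation bullets, and checks onset against resolution only when the onset date is fully missing

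*SAP*

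**What the plan says.** SAP 7.2.4 starts from a principle: "partial start dates of AEs will be assumed to be the closest possible date to date of first dose", provided the result agrees with what was recorded. Four bullets follow, and three of them matter here.

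- **Fully missing onset:** the date of first dose is used, followed by a check: "If the resulting onset date is after a reported date of resolution, the onset date will be set equal to the date of resolution". No other bullet carries this check.
- **Second bullet**, opening "If year is present, but both month and day are missing, or month is present, and day is missing": if the AE year equals the year of first dose, "set missing month to the month of first dose and missing day to the day of first dose".
- **Third bullet**, opening "If year and month are present, but day is missing": "if date of year and month > date of year and month of first dose, then set missing day to" the 1st of that month. An earlier month takes its last day, and the month of first dose takes the day of first dose.

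The section limits the imputed date to deciding TEAE status and keeps the recorded partial date in the listings. On the end of the window, SAP 13.1 says "All AEs will be captured up through day 56", and Protocol 16.4.2 runs the TEAE definition from first dose through the safety evaluation period, which ends at Day 56. SAP Section 7, in its general list, rules out imputation of missing or partial data altogether.

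**The concern.** An onset with year and month recorded and day missing satisfies the opening condition of both the second and the third bullet. Two programmers could each follow the text and derive different onset dates. Because the imputed date exists only to decide TEAE status, the question is whether the two dates can fall on opposite sides of a boundary. At the end of the window they can.

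The resolution check raises a separate problem that does not depend on which bullet is chosen. A partly dated event that began and ended before treatment can be moved onto the dosing day, after its own recorded end.

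TEAE tabulations are the planned AE presentation (SAP 13.1, Protocol 16.4.2), and dose-escalation cohorts have 3 to 6 subjects, so a single misclassified event would be visible.

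**Working it through.** The documents give no figure on this point to reproduce, so the rules were applied as written. First study drug falls on Day 0 in both arms (veledimex before craniotomy in Arm 1, the injection in Arm 2), so study day = onset date minus date of first dose.

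**1. Where the bullets differ.** They agree when the AE is in the month of first dose or in a different year. They differ when the AE is in the same year but another month.

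**2. Example.** First dose 20 March. There are 11 days to 31 March and 30 in April, so 30 April is Day 41 and Day 56 is 15 May.

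| AE recorded as | Second bullet | Third bullet |
|---|---|---|
| April | 20 April = Day 31 | 1 April = Day 12 |
| May | 20 May = Day 61 | 1 May = Day 42 |

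April is within Day 56 either way. May is within it only under the third bullet.

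**3. General case.** For the month after first dose, the second bullet gives a day equal to the length of the first-dose month, 28 to 31, so status does not change. For two months after, it gives the combined length of the first-dose month and the next:
- shortest: 31 + 28 = 59 (January to March, non-leap year)
- longest: 31 + 31 = 62 (July to September)

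Every valid date of this second kind is therefore past Day 56 and before Day 63. Some dates do not exist: first dose 31 March with an AE in April gives 31 April.

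**4. Exempt months.** With first dose in November or December, an onset two months later is in the next year, and both bullets give the 1st. First dose 10 November, AE in January: 20 + 31 + 1 = Day 52 under either.

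**5. Reach of the rule.** All first-dose dates in 2020–2021 (an assumed range) were crossed with all true onsets on Days 0 to 56, taking the day as missing: 731 × 57 = 41,667 combinations.
- The bullets give different valid dates in 62.3%.
- The second bullet passes Day 56 in 6,792 / 41,667 = 16.3%. This is possible for 69.9% of first-dose dates.
- The second bullet gives a non-existent date in a further 1.0%.
- The third bullet passes Day 56 in 0, and the second bullet passes Day 63 in 0.
- For recorded months before dosing, TEAE status never differs between valid dates.

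**6. Resolution check.** First dose 20 March, onset recorded as March, resolved 10 March. Both bullets give 20 March, ten days after resolution, and the event counts as a TEAE. With the check applied, onset becomes 10 March and the event is pre-dose. A year-only onset in the dosing year that resolved before dosing fails in the same way under the second bullet.

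**The case against.** The strongest answer is that the section settles the overlap itself. The opening principle and the more specific third bullet point the same way, and a non-existent date cannot be the nearest possible one. That stands as evidence of intent. It makes the overlap a drafting slip, but it does not state precedence for a programmer working from the bullets.

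A reader might infer that the plan as written removes AEs from the TEAE count. The documents do not support that. SAP 7.2.4 never says to test an imputed date against Day 56, and the schedule footnotes in both documents end recording at the Day 56 visit, which has a ±7-day window and so may be held up to Day 63. On that reading, or with no upper limit, nothing is lost.

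A reader might also take 16.3% or 69.9% as an expected effect. They are not forecasts. They assume evenly spread dosing and onset dates and concern only AEs with a missing day. Daily patient contact through Day 14 should make such records uncommon.

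Nor do the documents support a claim that events vanish or that dose decisions change. The primary endpoint is worded as the AE rate and DLTs, all AEs are listed for the Overall Safety Population, listings show dates as recorded, and the imputed date is not used for DLTs.

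The resolution problem is narrow as well. Under Protocol 14.5, events starting before study drug are reported as AEs only if protocol-related; otherwise they go to medical history.

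**Conclusion.** The point holds as a minor defect in stated rules, in two parts.

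- **Overlap.** The two bullets give conflicting dates for the same record. TEAE status changes only if the second bullet is used, a strict nominal Day 56 limit is applied to the imputed date, and the recorded month is two after the first-dose month in the same year (or the imputed date does not exist). First doses in November and December are unaffected.
- **Resolution check.** This error needs no choice between bullets and no upper limit. A partly dated, protocol-related event that resolved before dosing, in the month of first dose (or, if only the year is known, in that year), is wrongly counted as a TEAE.

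Few AEs should meet either set of conditions. The documents give no rate of partial dates, so no count of affected events can be estimated.

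**What to change.** Three text edits to the SAP before database lock:

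1. In 7.2.4, remove from the opening condition of the second bullet the alternative for a known month with a missing day, so that the third bullet alone handles that case. Nothing intended is lost.
2. Move the resolution-date check out of the fully missing bullet and apply it to every imputed onset.
3. In Section 7, make the 7.2.4 date rules an explicit exception to the statement that nothing is imputed.

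The cost is a few lines of text. No extra data are needed and the programming effort is negligible.

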### **7.2.5. Handling of Partial Dates for Medications**

When determining prior or concomitant medications, partial start dates of prior and concomitant medications will be assumed to be the earliest possible date consistent with the partial date. Partial stop dates of prior and concomitant medications will be assumed to be the latest possible date consistent with the partial date.

- For Start Date,
  - If the start date is completely missing, then the start date will not be imputed. Medication will be assumed to be prior medication.
  - If the year is present and month or day are missing, then set missing month to January and missing day to 1st of the month.
- For End Date,
  - If the end date is completely missing, then the end date will not be imputed. Medication will be assumed to be ongoing.
  - If the year is present and the month or day are missing, then set missing month to December and missing day to last day of the month.

## **8. PROTOCOL DEVIATIONS**

A protocol deviation is any change, divergence, or departure from the study design or procedures defined in the protocol.

- Important protocol deviations are a subset of protocol deviations that may significantly impact the completeness, accuracy, and/or reliability of the study data or that may significantly affect a subject's rights, safety, or well-being.
- Where applicable, important protocol deviations will be categorized as major protocol deviations.
  - Protocol deviations that are not deemed important protocol deviations are classified as minor protocol deviations
- The list of protocol deviations along with whether the deviation is classified as major or minor will be finalized prior to database lock.

No subject will be removed from any analysis population because of a protocol deviation.

In accordance with ICH E3, subject eligibility violations and important post- treatment protocol deviations will be identified and listed by subject ID and study center. Major deviations that are considered to potentially impact the efficacy or safety analyses will be tabulated. Important protocol deviations will be identified prior to database lock. Protocol deviations will be listed and summarized by type.

- Deviation from inclusion/exclusion criteria
- Withdrawal criteria met during the study but subject ID was not withdrawn
- Prohibited concomitant medications
- Treatment deviation
- Other protocol deviation

## 9. SUBJECT DISPOSITION

### Subject Disposition

The completion status of subjects treated by any experimental treatments will be summarized overall and by treatment arm and dose cohort based on the OSP. The primary reasons for treatment and study discontinuation will be summarized by treatment arm and dose cohort based on the OSP.

Subjects who are screen failures are not subjects that are treated on any study treatment and are only counted as the part of the subject disposition denoted as screened and not treated.

## 10. DEMOGRAPHICS AND BASELINE CHARACTERISTICS

### 10.1. Demographic and Baseline Characteristics

Demographic and baseline characteristics will be listed and described by subject ID (instead of being tabulated using descriptive statistics by treatment arm and dose cohort) for the OSP.

- Demographic variables include:
  - Age (years)
  - Sex
  - Race
  - Ethnicity
- Baseline characteristics include:
  - Height (cm)
  - Weight (kg)
  - BMI (body mass index, kg/m^2, calculated as Weight (kg) / Height (m))
  - ECOG performance status, KPS, lansky

Conversions for Height and Weight are as follows:

Height (cm) = Height (inches) x 2.54

Weight (kg) = Weight (lb) x 0.4536

## 10.2. Medical History

The medical history will be coded using the current version of the Medical Dictionary for Regulatory Activates (MedDRA). Originally, the frequency count and percentage of subjects who experience any medical conditions were to be tabulated by system organ class (SOC) and preferred term (PT) of MedDRA for all subjects and by treatment arm and dose cohort for the OSP. Instead, medical history, will be listed and described by subject ID.

If the same PT or SOC is reported more than once for a subject ID, the subject ID will only count once in the corresponding incidence of PT or SOC.

Listings will be presented by treatment arm, dose cohort, and subject ID for the EP.

## 10.3. Prior Therapies/Surgeries

Listings will be presented by treatment arm and dose cohort, by subject ID for the EP. Listings will summarize prior therapies, surgeries, and/or concomitant disease by treatment arm and dose cohort for the OSP

- (instead of Frequency counts and percentages for the summary of prior therapies, surgeries or concomitant disease by treatment arm and dose cohort for OSP).
- The therapies/surgeries with the same sequence/regimen number are counted as one prior therapy/surgery.

Where applicable, the following variables may be included as part of the subject listing:

- Relevant Disease under study
  - Any relevant past or concomitant disease
  - Most severity/CTCAE grade
- Surgery History
  - Any relevant past surgeries
  - Most severity/CTCAE grade
- Brain tumor diagnosis
  - Initial grade
  - Initial MGMT gene promoter status
  - Initial IDH status
  - Current disease status
  - Current grade
  - Current MGMT gene promoter status
  - Current IDH status
- Prior cancer treatment
  - Any cancer related therapy

- Treatment type
- Best response
- Disease under study

If the subject experienced multiple surgeries, the most severe grade will be used for the summary.

#### **10.4. Prior and Concomitant Medications/Procedures**

All medications as documented by Investigator will be coded using the World Health Organization Drug Dictionary (WHODrug, Sept 2016).

Prior medications are defined as medications that were started before the start of the study treatment and either ended before the start of the study treatment or continued after study treatment.

Concomitant medications are defined as non-study medications that were either initiated before study treatment and continued during the study treatment or initiated on/after study treatment but within the initial follow-up period (through Day 56).

In general, listings by treatment arm and dose cohort, and subject ID for concomitant medications and concurrent Medical Procedures will be provided for the OSP (instead of using frequency tables).

The prior and concomitant medications will be tabulated by subject ID, along with the treatment arm and dose cohort, ATC term 2 and the Preferred term for OSP.

- If the start and stop dates of the concomitant medications do not clearly define the period(s) during which a medication was taken, it will be assumed to have been a concomitant medication.
- For summary listings, if a subject has taken a medication more than once, the subject will be only counted once for the medication.
- Medications initiated prior to the start of first dose of study drug and are continued after the first dose of study drug will be counted as both prior and concomitant medications.

#### **11. DOSE LIMITING TOXICITIES (DLT)**

In general, listings by subject ID for DLT data by treatment arm and dose cohort, will be provided for the ESP.

The number of DLTs and the proportion of subjects with any DLT and each type of DLT will be summarized by treatment arm and dose cohort for the ESP if applicable.

## **12. RECOMMENDED PEDIATRIC PHASE II VELEDIMEX DOSE**

The recommended pediatric Phase II dose in the study will be determined in the context of variable corticosteroid exposure and other factors.

Where applicable, listings along with descriptive statistics will be used to tabulate the total corticosteroid daily dose (mg) by arm and dose cohort, and visit for the ESP.

As originally planned, listings including demographics could be provided for the total corticosteroid daily dose by arm and dose cohort, visit and subject ID for the OSP.

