7.5. Recommended Phase II Pediatric Veledimex Dose and Corticosteroid Exposure

The recommended Phase II pediatric veledimex dose will be determined using the Evaluable Safety Population (ESP). The recommended pediatric Phase II dose is defined as the dose level below the dose in which $\geq 33\%$ of subjects in the same cohort experience DLTs. If 2 DLTs occur in the same cohort, dose escalation will stop in the cohort experiencing the DLTs. A decision to enroll additional subjects in an expansion cohort will be made by the SRC.

The recommended pediatric Phase II dose in this study will be determined in the context of variable corticosteroid exposure and will be reported as such. Investigational treatment requires that steroid use be allowed to manage brain tumor related symptoms or edema, especially after tumor resection. It is expected that the use and dose of corticosteroids will vary among trial sites and among subjects, and therefore, the extent and dose of steroids is not specified in this protocol. The treating physician should consider the minimum starting steroid dose for study subjects, if determined that it is safe and appropriate for that individual subject. For study subjects who require a higher starting steroid dose, efforts should be made to taper steroids to the lowest amount that controls the subjects' symptoms, as determined to be safe and appropriate by the treating physician.

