8. SELECTION AND WITHDRAWAL OF SUBJECTS

8.1. Inclusion Criteria

The eligible study population includes pediatric subjects with a) recurrent or refractory supratentorial brain tumors, not in direct continuity with the ventricular system, that are unresponsive to conventional treatment or for which there is no alternative curative therapy (Arm 1) and b) non-disseminated DIPG post prior standard focal radiotherapy and for which a biopsy has previously been obtained (access to results required; access to tissue preferred) (Arm 2).

Inclusion Criteria:

1. Male or female subjects ≤ 21 years-of-age with the demonstrated ability to swallow capsules whole and who are willing to provide access to previously obtained biopsy results
2. Provision of written informed consent and assent, when applicable, for tumor resection, stereotactic surgery, tumor biopsy, sample collection, and/or treatment with study drug prior to undergoing any study-specific procedures
3. **Arm 1:** Evidence of recurrent or progressive supratentorial tumor, which has shown a $> 25\%$ increase in bi-dimensional measurements by MRI or is refractory with significant neuro-deterioration that is not otherwise explained with no known curative therapy, not in direct continuity with the ventricular system (e.g., there is physical separation between the tumor and ventricle, the tumor does not open directly into the ventricular system).
4. **Arm 2:** Clinical presentation of DIPG and compatible MRI with approximately 2/3 of the pons included and without evidence of dissemination. Subjects should be ≥ 2 weeks and ≤ 10 weeks post standard focal radiotherapy (*i.e.*, dose of 5400 to 5960 cGy and maximum dexamethasone of 1 mg/m²/day).
5. At the time of registration, subjects must have recovered from the toxic effects of previous treatments, as determined by the treating physician. The washout periods from prior therapies are intended as follows (windows other than what is listed below should be allowed only after consultation with the Medical Monitor):
 - a. Targeted agents, including small-molecular tyrosine kinase inhibitors: 2 weeks
 - b. Other cytotoxic agents: 3 weeks
 - c. Nitrosoureas: 6 weeks
 - d. Monoclonal antibody immunotherapies (*e.g.*, PD-1, CTLA-4): 6 weeks
 - e. Vaccine-based and/or viral therapy: 3 months
6. On a stable or decreasing dose of dexamethasone for the previous 7 days
7. Able to undergo standard MRI scans with contrast agent before enrollment and after treatment

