11.1. Permitted Medications

Subjects may receive standard treatments, including palliative and supportive care for any illness or symptom management during study treatment, including:

- Corticosteroids are permitted for brain tumor related symptoms. The treating physician should consider the minimum steroid dose for study subjects, if determined that it is safe and appropriate for the individual subject. For study subjects who require a higher steroid dose, efforts should be made to taper steroids to the lowest amount that controls the subject's symptoms, as determined to be safe and appropriate by the treating physician.
- Antidiarrheal therapy is permitted
- Anti-emetics are permitted for nausea and vomiting

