#### **4.4. Recommended Pediatric Phase II Veledimex Dose**

The recommended pediatric Phase II veledimex dose will be determined using the Evaluable Safety Population (ESP) which is defined in [Section 5](#).

- The recommended pediatric Phase II dose is defined as the dose level below the dose in which  $\geq 33\%$  of subjects in the same cohort experience DLTs. If 2 DLTs occur in the same cohort, dose escalation will stop in the cohort experiencing the DLTs.

The recommended pediatric Phase II dose will also be determined in the context of variable corticosteroid exposure and will be reported as such.

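### Steroid exposure, the stated context for the recommended Phase II dose, is summarised in total mg/day with no reference steroid and no BSA scaling, so small-cohort figures cannot be reliably compared

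*SAP*

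**What the plan says.** Protocol 7.5 states that the recommended dose "will be determined in the context of variable corticosteroid exposure and will be reported as such". SAP 4.4 repeats this, and SAP 12 says the dose "will be determined in the context of variable corticosteroid exposure and other factors".

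The planned display is in SAP 12. Where applicable, listings and descriptive statistics "will be used to tabulate the total corticosteroid daily dose (mg) by arm and dose cohort", and by visit, for the Evaluable Safety Population (ESP). A listing for the Overall Safety Population is optional.

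The protocol does not standardise on-study steroid use. Protocol 7.5 says "It is expected that the use and dose of corticosteroids will vary among trial sites and among subjects" and "the extent and dose of steroids is not specified in this protocol". Protocol 11.1 gives a class-wide permission: "Corticosteroids are permitted for brain tumor related symptoms".

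The documents scale by body size elsewhere. The Arm 2 entry criterion in Protocol 8.1 is set per m² of a named agent, "maximum dexamethasone of 1 mg/m²/day". Veledimex has a mg/m² target in Protocol Table 4b, and SAP 13.2.2 divides the administered veledimex dose by BSA. No section of either document converts one corticosteroid to another or expresses on-study steroid dose per m².

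**The concern.** A milligram of steroid is not a common unit here. The same mg/day is a different exposure in a small child and in a 21-year-old, and a milligram of one corticosteroid need not equal a milligram of another. The cohorts are small, so balance in body size or choice of agent cannot be relied on.

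The table has a purpose. It is the only steroid-specific summary planned to give the context in which the recommended dose is to be read. If cohort 4 (20 mg) looks more or less steroid-exposed than cohort 3 (10 mg) only because its subjects are larger or smaller, a reader could draw the wrong conclusion about how far steroids coloured the tolerability seen at each dose. Nor can the mg figures be set against the protocol's own mg/m² entry limit.

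**Working it through.** The plan states no figure for this point, so there is nothing to reproduce. The check uses the plan's own BSA limits.

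**Inputs**
- Conformant BSA, 20 mg cohort (Protocol Table 4b): 0.5 to 2.53 m², apart from 0.64 to 0.75, where the listed doses fall outside 75–125% of target.
- Conformant BSA, 10 mg cohort (same table): 0.76 to 1.26 and 1.51 to 2.53 m².
- Cohort size: 3 to 6 (Protocol synopsis, Sample Size Determination).
- Ratio R, the mg of another agent needed to match 1 mg of the reference: not in the documents. Assumed, range 1 to 10.

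**1. Range from body size alone.** Since mg/day = mg/m²/day × BSA, subjects on the same scaled dose differ in mg by the ratio of their BSAs.
- 20 mg cohort: 2.53 / 0.5 = 5.06-fold.
- 10 mg cohort: 2.53 / 0.76 = 3.33-fold.
- Conversely, 1 mg/day is 1 / 0.5 = 2.0 mg/m² at the lower limit and 1 / 2.53 = 0.40 mg/m² at the upper.

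**2. Cohort means with equal scaled exposure.** Take two illustrative three-subject cohorts, all at 1 mg/m²/day.
- BSA 0.76, 1.00, 1.26: mean 3.02 / 3 = 1.01 mg/day.
- BSA 1.51, 2.00, 2.53: mean 6.04 / 3 = 2.01 mg/day.

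The mg means differ two-fold although scaled exposure is identical.

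**3. Reversal.** Let the larger subjects be the 10 mg cohort at 1.0 mg/m²/day and the smaller ones the 20 mg cohort at 1.5 mg/m²/day. All six BSAs are conformant for their cohort.
- 10 mg cohort: doses 1.51, 2.00, 2.53; mean 2.01, median 2.00 mg/day.
- 20 mg cohort: doses 1.14, 1.50, 1.89; mean 4.53 / 3 = 1.51, median 1.50 mg/day.

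The cohort with 50% more scaled exposure is lower on the mean, median, minimum and maximum. The absolute level does not matter. With a constant scaled dose within each cohort, the means reverse whenever the ratio of scaled doses (here 1.5) is above 1 but below the inverse ratio of mean BSAs (here 6.04 / 3.02 = 2.0). At 0.4 and 0.6 mg/m²/day, both below the Arm 2 entry limit, the means are 0.81 and 0.60 mg/day.

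**4. Mixing agents.** If k of n subjects take an agent needing R times the mg for equal effect, and the other mg doses are equal, the cohort mean is multiplied by (n − k + kR) / n.
- One of three: 1.00 (R = 1), 1.33 (R = 2), 2.33 (R = 5), 4.00 (R = 10).
- One of six: 1.00, 1.17, 1.67, 2.50.

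These show sensitivity to R. They do not estimate what will happen in this trial.

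**The case against.** The strongest reply is that a reader will have the raw material. SAP 6.1 says summaries of very small samples will be avoided in favour of subject listings. SAP 10.4 tabulates medications by subject with ATC and preferred term, and SAP 10.1 and 13.5 list height and weight. With 3 to 6 subjects, each dose can be related to its drug and body size by hand. That stands, and it is why a reader who inferred that the cohorts cannot be compared at all would go too far. It does not repair the cohort statistics that SAP 12 still plans.

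A reader might also infer that the SAP prescribes a raw sum of milligrams across agents. It does not say how the total is formed. An unconverted sum is the natural reading of a total in mg, but it is implied, not stated. Display details are left to a separate Tables, Listings and Figures spreadsheet that is not among the documents. A conversion could be there, although the SAP does not say so and a derivation rule belongs in the SAP.

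The only corticosteroid the documents name is dexamethasone. If every subject takes it, the mixing problem disappears and only the body-size problem remains.

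SAP 7.1 also reports the median, quartiles and range, which limits the pull of one outlier. It does not help when body size differs across a whole cohort, as step 3 shows.

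Finally, steroids are tapered to symptoms, not prescribed per m², and the mg/m² limit applies only at Arm 2 entry. That is a fair reason to keep raw mg as well. It does not make raw mg comparable across body sizes.

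**Conclusion.** The concern holds as a reporting weakness that should be corrected. The plan gives steroid exposure a stated role in interpreting the recommended dose, then summarises it in a unit that cohorts of 3 to 6 cannot be relied on to share.

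The 5.06-fold and 3.33-fold figures are ratios between individuals at the limits of each cohort's BSA range. A reader might take five-fold as the expected error in a cohort comparison, or as applying to both dose levels. Neither follows. In the 10 mg cohort, 0.5 to 0.75 m² is outside the dosing tolerance, and Protocol 7.1 has such subjects analysed separately. The two-fold gap in means and the reversal come from illustrative cohorts sorted by size. They show what is possible, not what is likely.

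A reader might also infer that the dose decision itself is compromised. The documents do not support that: the recommended dose is defined by the proportion of subjects with DLTs (Protocol 7.5, SAP 4.4), escalation follows Protocol Table 5, and steroid exposure is descriptive context. The DLT rule, sample size and error rates are unaffected.

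The conclusion assumes that the ESP is limited to BSA-conformant subjects, as the protocol defines it (SAP 5.3 does not repeat that condition), and that no conversion is specified outside the two documents. The effect of mixed agents cannot be sized from the documents.

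**What to change.** In SAP 12, define the summary variable as daily corticosteroid dose in mg/m² of a named reference corticosteroid, for example dexamethasone-equivalent. Fix the conversion table in the SAP before database lock. Compute BSA from screening height and the latest available weight. Tabulate this variable by arm, dose cohort and visit for the ESP, and keep the raw drug and mg in the subject listing so that any conversion can be checked.

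The cost is one derived variable and reliance on a conventional conversion table. Height at screening, weight by visit and concomitant medications through Day 56 are already scheduled, and the planned mg table already needs drug doses. This changes reporting only and implies no view on any steroid dose.
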